### 3.2 Part B

Part B is a multiple ascending dose study design. Subjects will receive either PK10571 or placebo. Approximately 24 subjects will be enrolled in Part B. Subjects will be enrolled in 3 cohorts of 8 subjects each.

Gossamer Bio, Inc.

The initial dose for Part B will be determined after review of the safety and pharmacokinetic data from Part A by the Safety Review Committee.

Data from the lower dose cohort will be analyzed before deciding whether to proceed with the higher dose cohort. Alternatively, a lower dose may be administered, depending upon review of previous cohort's safety and pharmacokinetic data.

Subjects will receive one of the treatments listed in Table 3. The assigned treatment will be given either as a single daily dose (QD), or divided into two daily doses (BID), or divided into three daily doses (TID; each dose to be separated by 6 hours on a given day).

Subjects will be assigned to either active treatment or placebo in randomized fashion.

Table 3Part B: Planned Doses for Cohorts 1–3

| Cohort                 | Test Formulation (n = 6) | Placebo (n = 2) |
|------------------------|--------------------------|-----------------|
| 1                      | PK10571 initial dose     | Placebo         |
| 2                      | PK10571 mid dose*        | Placebo         |
| 3                      | PK10571 high dose*       | Placebo         |
| n = number of subjects |                          |                 |

n = number of subjects

Note: The dosing regimen will be either once daily (QD), twice daily (BID), or three times daily (TID) for 7 consecutive days. For TID dosing, each daily administration will be separated by 6 hours.

\* Alternately, Cohort 2 or 3 will receive a lower dose, depending upon safety and pharmacokinetic data from Cohort 1 or 2, respectively.

Each dose will be administered using an oral inhalation device. Meals will be the same and scheduled at approximately the same times relative to dose for each cohort, if possible. Refer to Section 5.5.1 for details regarding timing of meals for each proposed dosing regimen (QD, BID, and TID).

No water may be consumed for 1 hour prior through 1 hour after each dose, except for 60 mL of room temperature water which will be given to subjects to rinse their mouths after dosing. Subjects will swish the 60 mL of water in their mouths then spit it out.

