### 5.6 Drug Administration

Worldwide Clinical Trials pharmacy staff will package and dispense the study treatment. Prior to dosing, subjects will receive training in use of the oral inhalation device as indicated in the Events Schedules (Section 12) or as needed if additional training is determined.

Details for dose preparation, device training, and dose administration will be provided in a separate pharmacy manual.

Each subject will receive an oral inhalation dose of the assigned treatment (active drug or placebo). All doses of investigational product will be administered under the supervision of clinical study personnel.

For QD dosing, the subjects will remain seated, except as otherwise required for study procedures or personal needs, for the first 4 hours after dosing. Subjects will not be allowed to lie down, except as directed by clinical staff secondary to adverse events (AEs), for the first 4 hours after dosing.

For BID and TID dosing, the subjects will remain seated, except as otherwise required for study procedures or personal needs, for the first 4 hours after the first morning dose on Day 1 and Day 7. For other doses, subjects will remain seated for at least 1 hour after dosing. During the times when subjects are to remain seated, they will not be allowed to lie down, except as directed by clinical staff secondary to adverse events (AEs).

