### 5.10 Safety Monitoring and Procedures

5.10.1 Vital Signs

A full set of vital signs (blood pressure, pulse rate, respiration rate, temperature, and pulse oximetry) will be measured at screening, at 0 hour (predose), and at the end-of-the study visit (Day 11 of Part A and Day 35 of Part B).

In Part A, blood pressure, pulse rate, and pulse oximetry will be measured at the following times:

• 10 minutes and 1, 2, 4, 8, 12, 16, 24, and 48 hours postdose

Note: The information in this section for Part B applies to QD dosing only. The timing of vital sign measurements for BID and TID dosing are provided in Appendix 4 and 5, respectively.

In Part B, blood pressure, pulse rate, and pulse oximetry will be measured at the following times:

- 10 minutes and 1, 2, 4, 8, 12, 16, and 24 hours after Dose 1
- 1, 2, and 4 hours after Doses 2-6
- 10 minutes and 1, 2, 4, 8, 12, 16, 24 hours after Dose 7
- Day 9 (prior to discharge)
- Day 10
- Day 14

At the screening visit, each subject will have blood pressure measured in both arms. If there is no significant difference (i.e., greater than 15 mmHg) between the systolic

Gossamer Bio, Inc.

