#### CONFIDENTIAL

31 Jul 2018

blood pressure in each arm at screening, then at other times the subject may have blood pressure measured in the dominant arm. Should one set of blood pressure measurements be out of range, the blood pressure reading will be repeated in the same arm.

For purposes of qualifying any given subject for study participation, out-of-range vital signs may be repeated once.

Additional vital signs measurements may be performed as deemed medically necessary by research personnel. All vital signs measurements will be taken after the subject has completed a minimum 3-minute sit.

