| Adverse event assessment n            |           |              | •            |         |            |           |           |         |         |         |         | - X      |          |          |          |          |          |         |   |   |   |    |    | → |

BUN = blood urea nitrogen; CR = creatinine; ECG = electrocardiogram; FSH = follicle-stimulating hormone; hr = hours; HIV = human immunodeficiency virus; INR = international normalized ratio; min = minutes; PK = pharmacokinetic; PPD = positive purified protein derivative skin test; PT = prothrombin time; PTT = partial thromboplastin time;  $T_{max}$  = time of maximum concentration; TSH = thyroid stimulating hormone

- a) A full set of vital signs (blood pressure, pulse rate, respiration rate, temperature, and pulse oximetry) will be measured at screening, at 0 hour (predose), and at the end-of-the study visit on Day 35. Blood pressure, pulse rate, and pulse oximetry will be measured 10 minutes after the first dose and at the following hours after the first dose: 1, 4, 8, 12, 16, 24, then daily on Days 3-9 (48, 72, 96, 120, 144, 168, 192, and 216 hours postdose) and at the outpatient visits on Day 10 and 14. At the screening visit, each subject will have blood pressure measured in both arms. If there is no significant difference (i.e., greater than 15 mmHg) between the systolic blood pressure in each arm at screening, then at other times the subject may have blood pressure measured in one arm.
- b) Physical examinations will be conducted for all subjects at screening, predose on Day 1, and on Days 2, 4, 7, 9, 14, and 35.

Gossamer Bio, Inc.

CONFIDENTIAL

31 Jul 2018

- c) All subjects will have ECGs performed at screening and at the following times (relative to the first dose): predose, 20 minutes postdose, 2, 4, 8, and 24 hours postdose, Day 9 (prior to check-out), Day 14, and at the end of the study.
- d) Pulmonary function tests (FEV1 and FVC; best of 3 reproducible maneuvers) to be performed using spirometry. Repeat spirometry will be allowed at the Investigator's discretion.
- e) To be performed at 1, 8, and 24 hours post Day 7 dose.
- f) PPD test to be read 48-72 hours after placement.
- g) Safety labs (chemistry, hematology, coagulation, and urinalysis) will be collected at the following time points: screening, check-in, Day 2, Day 4, Day 7, Day 9, Day 14, and Day 35 (end of study)

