a: A full set of vital signs (blood pressure, pulse rate, respiration rate, temperature, and pulse oximetry) will be measured at screening, predose on Day 1, and at the end-of-the study visit on Day 35. Blood pressure, pulse rate, and pulse oximetry will be measured on Day 1 and Day 7 (times relative to the first dose of the day) at 10 minutes and 1, 4, 8, 12, 16, and 24 hours postdose, daily (predose) on Days 3-6 and 7-9, and at the outpatient visits on Day 10 and 14. At the screening visit, each subject will have blood pressure measured in both arms. If

Gossamer Bio, Inc.

CONFIDENTIAL

31 Jul 2018

there is no significant difference (i.e., greater than 15 mmHg) between the systolic blood pressure in each arm at screening, then at other times the subject may have blood pressure measured in one arm.

- b: Physical examinations will be conducted for all subjects at screening, before the first dose on Day 1, and on Days 2, 4, 7, 9, 14, and 35.
- c: All subjects will have ECGs performed at screening and at the following times on Day 1 and Day 7 (times relative to the first dose of the day): predose, 20 minutes postdose, 2, 4, 8, and 24 hours postdose, Day 9 (prior to check-out), Day 14, and at the end of the study.
- d: Chest x-ray will be performed on Day 35 if clinically indicated as determined by the Investigator.
- e: Pulmonary function tests (FEV1 and FVC; best of 3 reproducible maneuvers) using spirometry will be performed at screening, check-in, at 1, 4, 8, and 23 hours after administration of the first and last morning doses (Day 1 and Day 7), at least 1 hour after the first dose on Day 4, on Day 14, and at the end of the study (Day 35). Repeat spirometry will be allowed at the Investigator's discretion.
- f: PPD test to be read 48-72 hours after placement.
- g: Safety labs (chemistry, hematology, coagulation, and urinalysis) will be collected at the following time points: screening, check-in, Day 2, Day 4, Day 7, Day 9, Day 14 and Day 35 (end of study)
- h: To be performed before the first dose of the day on Day 1 and 10 minutes after the first dose of the day (or Tmax, based on analysis from previous cohort) on Day 1 and Day 7.
- i: To be performed before the first dose of the day on Day 1 and 5 minutes after the first dose of the day (or Tmax, based on analysis from previous cohort) on Day 1 and Day 7.

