|---|-----------|--------------|--------------|--------|------------|---------|---------|--------|--------|--------|--------|--------|--------|---------|---------|---------|---------|---------|---------|---------|----------------|---|---|---|----|----|------------------|
| Part B - TID                                | -28 to -1 | -1           |              |        |            |         |         |        |        |        | 1      |        |        |         |         |         |         |         |         | 2       | 3
to
6   | 7 | 8 | 9 | 10 | 14 | 35               |
| Procedure                                   | Screening | Check-
in | Pre-
dose | 0
h | 3/5
min | 10
m | 20
m | 1
h | 2
h | 4
h | 5
h | 6
h | 8
h | 10
h | 12
h | 16
h | 20
h | 23
h | 24
h | 36
h |                |   |   |   |    |    |                  |
| Informed consent                            | X         |              |              |        |            |         |         |        |        |        |        |        |        |         |         |         |         |         |         |         |                |   |   |   |    |    |                  |
| Demographics
and smoking
history      | Х         |              |              |        |            |         |         |        |        |        |        |        |        |         |         |         |         |         |         |         |                |   |   |   |    |    |                  |
| Medical and
medication
histories      | X         |              |              |        |            |         |         |        |        |        |        |        |        |         |         |         |         |         |         |         |                |   |   |   |    |    |                  |
| Concomitant
medication
review         | х         |              |              |        |            |         |         |        |        |        |        |        |        |         |         |         |         |         |         |         |                |   |   |   | х  | х  | X                |
| Vital signs and pulse oximetry a | X         |              | Х            |        |            | Х       |         | х      | Х      | Х      |        |        |        |         | Х       | х       |         |         | х       |         | Х              | Х | Х | Х | Х  | Х  | Х                |

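### If Part B uses BID or TID, at most one Day 2–6 dose has a blood pressure, pulse and oximetry set scheduled in the next 4 h, and the QD schedule contradicts itself

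*Protocol*

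**What the plan says.** - **Which text governs.** The Part B times in Protocol Section 5.10.1 are for QD only. For the other regimens it says: "The timing of vital sign measurements for BID and TID dosing are provided in Appendix 4 and 5, respectively".
- **BID and TID.** Footnote a of Table 9 (Appendix 4) and of Table 11 (Appendix 5) sets readings on Days 1 and 7 at 10 min and 1, 4, 8, 12, 16 and 24 h from the first dose of the day. The rest are taken "daily (predose) on Days 3-6 and 7-9, and at the outpatient visits on Day 10 and 14". No separate Day 2 set is listed; the only one is the Day 1 24 h set.
- **Dose times.** BID doses are 12 h apart (Appendix 4). Section 3.2 says: "For TID dosing, each daily administration will be separated by 6 hours". It also describes BID and TID as dividing the assigned treatment over the day.
- **QD, Section 5.10.1.** Readings are due "1, 2, and 4 hours after Doses 2-6", with a timed profile from 10 min to 24 h after Dose 7.
- **QD, Table 7 footnote a.** After the Day 1 profile the readings are "then daily on Days 3-9 (48, 72, 96, 120, 144, 168, 192, and 216 hours postdose"). There are no 1, 2 and 4 h sets after Doses 2–6 and no timed profile after Dose 7.
- **TID grid.** In Table 11, as extracted, the vital-signs row marks 10 min and 1, 2, 4, 12, 16 and 24 h on Day 1. Footnote a lists 8 h and omits 2 h.
- **Use of the data.** Change in vital signs is a named safety endpoint (SAP 3.1). Vital signs are reviewed before each escalation (Protocol Section 3.3). SAP 6.2.9 tabulates scheduled values only; post-baseline unscheduled readings are listed.

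**The concern.** This is a first-in-human study of an inhaled drug given repeatedly for seven days. Under BID or TID, five of those days have no timed reading of saturation or blood pressure soon after a dose, and the protocol gives no reason. The mid-course readings that do exist are taken before the first dose of the day, furthest from the previous dose. A brief fall without symptoms, appearing or growing as doses repeat, would not be looked for between Day 1 and Day 7. It would also be missing from the tabulated vital-sign changes unless someone happened to take an extra reading, and that reading would only be listed.

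Two conflicts add to this. A QD site cannot tell from the protocol whether Section 5.10.1 or Table 7 footnote a applies. A TID site that follows the Table 11 grid would skip the only Day 1 reading between the 6 h and 12 h doses.

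**Working it through.** **1. QD figure under Section 5.10.1.** 3 times × 5 doses (Doses 2–6) = 15 sets, covering 5 of 5 doses.

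**2. Dose times** in hours from the first Day 1 dose, for day d: BID at 24(d−1) + {0, 12}; TID at 24(d−1) + {0, 6, 12}. On Days 2–6 that is 2 × 5 = 10 BID doses and 3 × 5 = 15 TID doses.

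**3. Scheduled sets in that period**, footnote a of Tables 9 and 11: the Day 1 set at 24 h, then one predose set per day at 48, 72, 96, 120 and 144 h.

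**4. Criterion.** A dose at time t is covered if a set falls at v with t < v ≤ t + 4. The 4 h limit is the last QD time after Doses 2–6 in Section 5.10.1.

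**5. Result for Days 2–6.**

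| Reading of the schedule | BID | TID |
|---|---|---|
| 24 h set taken before the Day 2 dose | 0 of 10 | 0 of 15 |
| 24 h set taken just after the Day 2 dose | 1 of 10 | 1 of 15 |
| Predose read as before every dose | 0 of 10 | 0 of 15 |

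In the first row, the next set comes 24 or 12 h after a BID dose (24→48, 36→48) and 24, 18 or 12 h after a TID dose (24→48, 30→48, 36→48). The zeros therefore hold for any window shorter than 12 h. In the third row, each set falls 12 h (BID) or at least 6 h (TID) after the previous dose, so it still misses the 4 h window.

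**6. Days 1 and 7.**
- BID: the 0 h dose has the 10 min, 1 h and 4 h sets and the 12 h dose has the 16 h set, so 4 of 4 doses are covered.
- TID: footnote a adds 8 h for the 6 h dose, giving 6 of 6. Under the grid the 6 h dose has no set up to 10 h, so coverage is 5 of 6 if only Day 1 follows the grid, and 4 of 6 if Day 7 does too.

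**7. QD under Table 7 footnote a alone.** The readings at 24, 48, 72, 96 and 120 h coincide with the nominal times of Doses 2–6, and the footnote does not say which comes first. Taken before the dose, they cover 0 of 5 doses (0 of 6 with Dose 7). Taken just after, they cover 5 of 5, but with 5 sets instead of 15. Neither reading gives the 1, 2 and 4 h sets of Section 5.10.1.

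**The case against.** - **The QD comparison is not secure.** A reader might infer that the protocol deliberately watches the more frequent regimens less closely than QD. The documents do not support that. Section 5.10.1 and Table 7 footnote a conflict, and if the footnote governs, most of the contrast goes. Table 7 footnote a also omits the 2 h Day 1 set marked in its own grid, but this does not show which text was intended: the Table 9 and 11 footnotes and the Table 9 grid omit 2 h too. This objection stands.
- **Units.** Setting 0 of 15 TID doses beside 15 QD sets would mislead. Like for like, QD is 5 of 5 doses under Section 5.10.1.
- **Lighter per-dose monitoring may be reasonable.** At a given daily dose, each BID or TID inhalation is a half or a third of the QD inhalation. The protocol does not offer this as its reason, but it is plausible.
- **Much is already in place.** Part A has vital signs from 10 min to 48 h after single doses, reviewed before Part B. Part B has sentinel subjects, timed profiles on Days 1 and 7, confinement to Day 9, supervised dosing, adverse event queries, and a physician on site for at least 4 h after dosing. Day 4 also has spirometry after the first dose, and extra vital signs may be taken if medically necessary. These should catch symptomatic events. They do not give a systematic post-dose reading in every subject.
- **No decision rule depends on it.** A reader might infer that the stopping rules are weakened. Section 3.5 has no rule that turns on an asymptomatic fall in saturation or blood pressure; its respiratory rule refers to desaturation with dyspnea.
- **The gap is conditional.** If every Part B cohort is dosed QD, it never arises.
- **The TID grid may be a slip.** The Table 11 grid also lacks the 8 h ECG mark that its footnote c lists, and it was read from extracted text. It still needs correcting.

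**Conclusion.** The concern holds in a limited form. If BID or TID is chosen, no Day 2–6 dose has a scheduled blood pressure, pulse and oximetry set in the following 4 h (BID 0 of 10, TID 0 of 15), or 1 in each if the 24 h set follows the Day 2 dose. This comes directly from footnote a of Tables 9 and 11 and does not depend on how the QD conflict is settled. The contrast with QD (5 of 5 doses) does: it holds only under Section 5.10.1.

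What is lost is systematic detection of asymptomatic, transient changes between Day 1 and Day 7. The gain from closing the gap is better safety data for the committee and the report. Priority is modest, and the case rests on low cost more than on a demonstrated hazard. The QD conflict and the missing 8 h mark in the TID grid should be resolved because they affect what the site does.

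**What to change.** 1. **BID and TID.** Keep the daily predose set and add at least one post-dose blood pressure, pulse and oximetry set on each of Days 2–6, for example about 1 h after a dose. Section 5.6 already keeps subjects in place: "For other doses, subjects will remain seated for at least 1 hour after dosing". On Day 4 the set can be taken with the spirometry. The sponsor's clinicians should choose the dose and time.
2. **QD.** Amend Table 7 footnote a to match Section 5.10.1 for Doses 2–7. The documents do not settle which was intended; Section 5.10.1 is the schedule that gives timed post-dose data.
3. **TID.** Align the Table 11 grid with footnote a so that the 8 h set is taken, and settle the 2 h set at the same time.
4. **Minor.** State whether the Day 1 24 h set precedes the Day 2 dose.

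**Cost.** Item 1 adds 5 sets per subject, 5 × 8 = 40 per cohort, and at most 40 × 3 = 120 if all three cohorts use BID or TID. Each takes a little nurse time in confined, seated subjects: "All vital signs measurements will be taken after the subject has completed a minimum 3-minute sit". No new equipment is needed. Extra readings bring some chance out-of-range values: if 1–5% of sets are flagged (an assumption), 40 × 0.01 to 40 × 0.05 = 0.4 to 2 per cohort. One set a day covers only 5 of 10 BID or 5 of 15 TID doses. Covering every dose would take 10 × 8 = 80 or 15 × 8 = 120 sets per cohort, which is harder to justify given the existing safeguards. Items 2–4 are text edits, although item 2 settles how many readings a QD site takes.

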## APPENDIX 5 PART B: MAD THREE TIMES DAILY (TID) DOSING

The Safety Review Committee will review the safety data (including local irritation) and pharmacokinetic data from the SAD protocol (Part A) to determine the starting dose for the first MAD cohort, and if the first cohort of the MAD protocol should be dosed QD (once daily), BID (twice daily; once every 12 hours), or TID (three times daily; 6 hours between each dose).

If the decision is made to start dosing in the MAD protocol at TID, then the Safety Review Committee will review the safety data (including local irritation) and PK data from the first MAD cohort to determine if TID dosing should continue, if dosing should be reduced to BID or QD for the next cohort. Similarly, if the starting dose in the MAD protocol is BID, then the Safety Review Committee will review the safety data (including local irritation) and PK data from the first MAD cohort to determine if BID dosing should continue, or if dosing should be changed to QD or TID for the next cohort.

## **Blood Sampling, Processing and Shipment**

A total of 180 mL (30 x 6 mL samples) will be collected from each subject in Part B for pharmacokinetic analysis.

In addition, approximately 173.5 mL of blood will be collected for laboratory evaluations. The total volume of blood collected from each subject will not exceed approximately 353.5 mL. Additional blood may be collected if necessary for repeat laboratory evaluations or AE follow up.

Blood samples collected up to and including 24 hours postdose within  $\pm 2$  minutes of scheduled time will not be considered deviations. Blood samples collected after 24 hours through 48 hours after the last dose within  $\pm 5$  minutes of scheduled time will not be considered deviations. Blood samples collected after 48 hours postdose after the last dose within  $\pm 10$  minutes of scheduled time will not be considered deviations.

| Reason for Collection  | Number of
Samples | Volume per
Sample (mL) | Total Volume (mL) |
|--|----------------------|---------------------------|-------------------|
| Clinical labs at screening                                     | 1                    | 25                        | 25                |
| Clinical labs during study (check-in, Days 2, 4, 7, 9, and 14) | 6                    | 15                        | 90                |
| Clinical labs end-of-study                                     | 1                    | 15                        | 15                |
| Platelet aggregation   | 3                    | 6.5                       | 19.5              |
| Buffy coat samples   | 3                    | 8                         | 24                |
| Pharmacokinetic analysis                                       | 30                   | 6                         | 180               |
|  |                      | Total                     | 353.5             |

Table 10 Total Amount of Blood to be Collected for Testing in Part B (TID Dosing)

|   |           |              |              |        |            |         |         |        |        |        | S      | Stud   | y D    | ay(s)   |         |         |         |         |         |         |                |   |   |   |    |    |                  |
|---|-----------|--------------|--------------|--------|------------|---------|---------|--------|--------|--------|--------|--------|--------|---------|---------|---------|---------|---------|---------|---------|----------------|---|---|---|----|----|------------------|
| Part B - TID                                | -28 to -1 | -1           |              |        |            |         |         |        |        |        | 1      |        |        |         |         |         |         |         |         | 2       | 3
to
6   | 7 | 8 | 9 | 10 | 14 | 35               |
| Procedure                                   | Screening | Check-
in | Pre-
dose | 0
h | 3/5
min | 10
m | 20
m | 1
h | 2
h | 4
h | 5
h | 6
h | 8
h | 10
h | 12
h | 16
h | 20
h | 23
h | 24
h | 36
h |                |   |   |   |    |    |                  |
| Informed consent                            | X         |              |              |        |            |         |         |        |        |        |        |        |        |         |         |         |         |         |         |         |                |   |   |   |    |    |                  |
| Demographics
and smoking
history      | Х         |              |              |        |            |         |         |        |        |        |        |        |        |         |         |         |         |         |         |         |                |   |   |   |    |    |                  |
| Medical and
medication
histories      | X         |              |              |        |            |         |         |        |        |        |        |        |        |         |         |         |         |         |         |         |                |   |   |   |    |    |                  |
| Concomitant
medication
review         | х         |              |              |        |            |         |         |        |        |        |        |        |        |         |         |         |         |         |         |         |                |   |   |   | х  | х  | X                |
| Vital signs and pulse oximetry a | X         |              | Х            |        |            | Х       |         | х      | Х      | Х      |        |        |        |         | Х       | х       |         |         | х       |         | Х              | Х | Х | Х | Х  | Х  | Х                |
| Physical examination b           | Х         |              | Х            |        |            |         |         |        |        |        |        |        |        |         |         |         |         |         | Х       |         | X b | Х |   | Х |    | Х  | Х                |
| 12-lead ECG c                    | Х         |              | Х            |        |            |         | Х       |        | Х      | Х      |        |        |        |         |         |         |         |         | Х       |         |                | Х | Х |   |    | Х  | Х                |
| Chest X-ray                                 | Х         |              |              |        |            |         |         |        |        |        |        |        |        |         |         |         |         |         |         |         |                |   |   | Х |    |    | $\mathbf{X}^{d}$ |
| Pulmonary
function tests e    | X         | Х            |              |        |            |         |         | Х      |        |        | х      |        |        |         |         |         |         | Х       |         |         | Х              | Х |   |   |    | Х  | Х                |
| $PPD^{f}$                                   | Х         |              |              |        |            |         |         |        |        |        |        |        |        |         |         |         |         |         |         |         |                |   |   |   |    |    |                  |
| TSH   | X         |              |              |        |            |         |         |        |        |        |        |        |        |         |         |         |         |         |         |         |                |   |   |   |    |    | Х                |
| HIV, hepatitis B and C                      | X         |              |              |        |            |         |         |        |        |        |        |        |        |         |         |         |         |         |         |         |                |   |   |   |    |    |                  |

